#### Table 4: Example analysis model RQ7

Analysis and	Level 1 (pupil)	Level 2 (school)	Outcome Variable
Sample	Covariates	Covariates	
Empty model			
ITT sample (RQ7)	Baseline variety of delinquency score (SRDS) (centred around the mean)	Mean school-level variety of delinquency score (SRDS) (centred around school level Grand mean)	Follow up variety of delinquency score (SRDS)
	Group (1=Reach participants school, 0=Control group participants)		

#### Subgroup analyses

The subgroup analysis was specified a priori and reflects the description of this analysis in the protocol. Exploratory analyses of sub-group will examine evidence of differential impact relating to YP ethnicity, gender and age of the YP. Sub-group analysis by ethnicity will further inform the RQs set out in the IPE which explore how far the intervention is reaching YP from ethnic minority backgrounds, and will allow an exploration as to whether outcomes differ by ethnicity. In terms of gender of the YP, the qualitative findings from the feasibility study showed that young males recruited to the Reach Programme responded well to a predominately female YW team, suggesting that the gender of the YW was less important in terms of responsiveness of male participants. Exploring this factor in the subgroup analysis will further inform this research question by allowing an exploration of any differences in outcomes between males and female participants. Findings from the feasibility study suggested that schools were keen to refer YP at the earliest point possible in their lives given that the Reach Programme is intended as a preventative intervention. Analysis of outcomes by age will allow insight into whether the Reach Programme shows any difference in outcomes for younger participants. The research questions for the sub-group analysis are set out below:

- **RQ12** Are any differences in the primary outcome (externalising score teacher report SDQ) observed with regards to the ethnicity of the YP?
- **RQ13** Are any differences in the primary outcome (externalising score teacher report SDQ) observed with regards to the sex of the YP?
- **RQ14** Are any differences in the primary outcome (externalising score teacher report SDQ) observed with regards to the age of the YP?

The final categories for ethnicity and age will be decided upon examination of the final achieved sample to inform the categories that contain sufficient numbers for analysis. Detailed data on these subgroups is being collected as part of the monitoring data, and will be matched into the final dataset.

As illustrated in Table 5 (using RQ13 as an example), subsample analyses will first be undertaken by including two additional variables to the model; a main effect term (i.e. ethnicity, gender or age) and an interaction between this and group membership. These analyses will directly examine evidence of differential impact for Reach. If the interaction term is found to be statistically significant, follow-on analyses will undertake separate impact analyses for the subsamples.

Analysis and Sample	Level 1 (pupil) Covariates	Level 2 (school) Covariates	Outcome Variable
Empty model			
ITT sample (RQ7)	Group (1=Reach participants school, 0=Control group participants) Baseline variety of delinquency score (SRDS) (centred around the mean) Sex (1=Female, 0=Male) Sex*Group interaction	Mean school-level variety of delinquency score (SRDS) (centred around school level Grand mean)	Follow up variety of delinquency score (SRDS)

#### Table 5: Example analysis model RQ13

#### Imbalance at baseline

Our examination of imbalance at baseline will focus on the baseline measures collected (described in table 1) and YP characteristics including age, gender and ethnicity. A table of baseline characteristics will be presented, showing counts and percentages for categorical variables, and means and standard deviations for continuous variables. These analyses will provide an indication of imbalance at baseline following randomisation. Effect sizes will be calculated from the descriptive statistics generated from scale variables and then used to determine where sensitivity analysis is needed. Austin (2009) suggests that a standardised

difference of 0.1 denotes meaningful imbalance, this is especially relevant if the variables in which imbalance is seen are highly predictive of outcomes (Ho et al., 2007). If imbalance at baseline is observed, a sensitivity analysis will be included to address this by including the variable (with observed imbalance) as a covariate as an efficient method for achieving better balance (Hewitt & Togerson, 2006).

#### **Missing data**

The baseline and ITT samples will be compared to help illustrate the impact of missing data for the primary outcome variable only. A summary of known reasons for missing data will be presented (e.g. YP moved school/YP excluded from school). This will firstly be done descriptively by tabulating missing cases across the categories of variables included in the ITT analysis. Reasons for any missingness will be summarised and we will examine whether missingness is associated with school and/or pupil-level covariates for example; baseline data. A multi-level logistic regression model (1=in ITT model; 0=not in ITT model) will examine whether missingness is associated with school or pupil-level covariates (including age/gender/ethnicity of the YP).

If over 5% of cases in the baseline sample are missing from the headline ITT analysis, we will adopt the following approach for screening and addressing missing data. Screening stage: We will examine whether data is missing completely at random (MCAP), missing at random (MAR) or missing not at random (MNAR). A series of binary variables will be generated for all variables in the final ITT analysis that measures whether a case is missing (=1) or not (=0). Logistic regression will be used to examine whether missing data can be statistically accounted for using the other variables in the ITT analysis. When variables are found to account for a statistically significant proportion of variation in missing data, we will proceed to one of the next two stages. For instances where only data is missing in the teacher report SDQ externalising score outcome measure, we will add any additional covariates that were found from the screening stage to the final ITT model and re-estimate the effect size. For instances where data is missing in the baseline measure and where the screening stage identified variables that did account for variation in this missing data, we will construct a Multiple Imputation model using all variables listed for stage 1. The Multiple Imputation model will be estimated using 'STATA MI' to create 20 imputed data sets. These imputed data sets will be used to re-estimate the effect of Reach and the standard error (Rubin, 2004).

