# Statistical analysis plan: The Reach

## Programme

Evaluating institution: Sheffield Hallam University Principal investigator(s): [name], [name] and [name]

Project title 	The Reach Programme	
Developer (Institution)	VRU for Leicester, Leicestershire and Rutland, Leicester City Council, Leicestershire County Council	
Evaluator (Institution)	Sheffield Hallam University	
Principal investigator(s)	[name], [name], [name]	
SAP author(s)	[name], [name]	
Trial design	Blocked Randomised Controlled Trial (RCT) design. Within each block (i.e. school), referred young people (YP) will be randomised to receive the Reach programme or BAU contro (i.e. two arms).	
Trial type	Efficacy with internal pilot	
Evaluation setting	School	
Target group	Children and YP aged 11 to 16 years old who are at risk of suspension or who are persistently absent from school, and where there are concerns about future involvement in anti- social behaviour and crime as both a victim or perpetrator.	
Number of participants	12 schools, 600 YP	

Primary outcome and data source	Externalising score (Teacher report SDQ)		
Secondary outcome and data source	
 
Internalising score (Teacher report SDQ)
 
Externalising score (Self report SDQ)
 
Internalising score (Self report SDQ)
 
Prosocial behaviour score (Teacher report SDQ)
 
Prosocial behaviour score (Self report SDQ)
 
Variety of delinquency score (SRDS)
 
Volume of delinquency score (SRDS)
 
Number of suspensions (source: Leicester City Council and Leicestershire County Council)
 
School attendance (source: Leicester City Council and Leicestershire County Council)
 
Offending data (source: VRU Leicester)
 
		

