### Introduction

The Reach Programme is targeted intervention aimed at YP (young people) aged 11-16 in secondary schools (years 7-11) who are at risk of suspension (i.e. they have carried out behaviour in their school that would normally qualify for a suspension) or who are persistently absent from school, have 3 indicators of vulnerability (e.g. looked after, domestic violence or substance misuse in the home) and where there are concerns about future involvement in anti-social behaviour and crime as both a victim or perpetrator. YP are referred to the Reach Programme directly from schools. A team of 10 Youth Workers working across the 12 schools deliver one to one sessions to YP over a period of 6 months, covering a set of core components as follows:

- Relationship Building
- Understanding behaviour
- Social Skills training
- Confidence, Wellbeing and Resilience
- Positive Family, Peer, and Community Relationships
- Identifying and Achieving Aspirations
- Recreational Activity

The Reach evaluation is designed as an efficacy trial with internal pilot. The internal pilot phase of the evaluation is now complete, and the efficacy phase began in January 2024 across the same 12 schools that were recruited for the pilot phase. Whist the sample of 12 schools remains the same, the YP recruited to the efficacy phase are different to those recruited at the pilot phase. Please see the Reach Protocol for a more detailed description of the intervention and associated documents (referral form, Theory of Change and Logic Model).

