# **Design overview**

#### Table 1: Design overview

Trial design, including number of arms		Two-arm randomised control trial		
Unit of randomisation		Individual participant		
Stratification variables (if applicable)		School (to balance allocation within schools)		
Primon	variable	Behavioural difficulties		
outcome	measure (instrument, scale, source)	Teacher report SDQ externalising score [0 to 20]		
Secondary outcome(s)	variable(s)	
 
Emotional regulation and peer relationships (Teacher report SDQ)
 
Behavioural difficulties (Self report SDQ)
 
Emotional regulation and peer relationships (Self report SDQ)
 
Prosocial behaviour (Teacher report SDQ)
 
Prosocial behaviour (Self report SDQ)
 
Variety of delinquency
 
Volume of delinquency
 
Number of suspensions
 
Attendance at school (%)
 
Level of offending
 
		
	measure(s) (instrument, scale, source)	
 
Teacher report SDQ internalising score [0 to 20]
 
Self report SDQ externalising score [0 to 20]
 
Self report SDQ internalising score [0 to 20]
 
Teacher report prosocial score [0 to 10]
 
Self report prosocial score [0 to 10]
 
Variety of delinquency (SRDS)
 
Volume of delinquency (SRDS)
 
Number of suspensions
 
Attendance at school (%)
 
Level of offending
 
		

Baseline for	variable	Behavioural difficulties	
primary outcome	measure (instrument, scale, source)	Teacher report SDQ externalising score [0 to 20]	
Baseline for secondary		
 
Emotional regulation and peer relationships (Teacher report SDQ)
 
Behavioural difficulties (Self report SDQ)
 
Emotional regulation and peer relationships (Self report SDQ)
 
Prosocial behaviour (Teacher report SDQ)
 
Prosocial behaviour (Self report SDQ)
 
Variety of delinquency
 
Volume of delinquency
 
Number of suspensions
 
Attendance at school (%)
 
Level of offending
 
	

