### Sample size calculations overview

The power calculations assume an ITT analyses with 100% complete baseline/outcome data and that the only systematic difference between the Reach group and the control group is their group membership (all other difference are random). Table 2 below presents the sample size calculations, showing firstly the estimates presented in the protocol from which the sample size for the study was drawn (600 YP) to achieve an MDES of 0.18 - 0.19. This was determined a priori using correlation estimates (0.50 to 0.60), drawn from the EEF Adventure Learning Trial (Willis et al., 2023), and drawing on the Reach baseline pilot data for the ICC (0.13). The sample size of 600 YP was discussed with the delivery partner and the timescales to achieve this sample size were agreed, also taking into account practical considerations in terms of delivery. Subsequent to this the internal pilot phase has now been completed, giving an updated participant level correlation of 0.32 (calculated from the full set of pilot data), which would achieve an MDES of 0.21 for the same sample size (Table 2).

Sample = 600 CYP across 24 clusters (25 CYP per cluster)		Protocol	Randomisation: drawing on Reach pilot data for ICC and correlation estimates*
Minimum Detectable Effect Size (MDES)		0.18-0.19 sds	0.21 sds
Pre-test/	level 1 (participant)	0.50 to 0.60	0.32 (R  =0.10)
post-test correlations	level 2 (cluster)	n/a 	n/a 
Intracluster correlations (ICCs)	level 1 (participant)	n/a²	n/a²
	level 2 (cluster)	0.13	0.13
Alpha 		0.05	0.05
Power		0.80	0.80
One-sided or two-sided?		Two	Тwo

Table 2: Sample size calculations

\*Internal pilot phase was completed subsequent to protocol submission and is drawn on to inform the SAP

The power calculations were undertaken using a formula and checked using the PowerUp software (Dong et al., 2013, sheet BIRA1\_1r). For the Reach evaluation, this is a blocked RCT

<sup>2 Dong, N., & Maynard, R. A. (2013). PowerUp!: A tool for calculating minimum detectable effect sizes and minimum required sample sizes for experimental and quasi-experimental design studies. Journal of Research on Educational Effectiveness, 6(1), 24-67.doi: 10.1080/19345747.2012.673143. https://www.causalevaluation.org/power-analysis.html

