#### Primary outcome analysis

The primary outcome measure for the Reach trial is behavioural difficulties as measured by the externalising score contained within the teacher version of the SDQ (Goodman, 2001). The SDQ, teacher version is a 25-item scale used to assess behaviour in the school context in 4–16-year-olds. This consists of 5 subscales; conduct problems, hyperactivity scale, emotional problems scale, peer problems scale and prosocial scale. The externalising score measures "behavioural difficulties" and is the sum of the conduct and hyperactivity scales. This links well with the Theory of Change in terms of improved behaviour management, reduction in negative behaviours in school and reduction in problem behaviours both in and out of school. This is also one of YEF's core outcome measures. The primary research question for the Reach trial is set out below:

**RQ1** What is the difference in behavioural difficulties measured using the externalising score from the teacher report Strengths and Difficulties Questionnaire (SDQ) between the intervention group, when compared to a 'business as usual' control?

Table 3 below provides an example analysis model for RQ1.

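### The plan gives exclusion from school as a reason for missing data but has no analysis for loss that depends on the teacher-rated outcome, so the Reach effect can be biased in either direction without correction

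*SAP*

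**What the plan says.** - **Outcome.** SAP Table 1 defines the primary measure as "Teacher report SDQ externalising score [0 to 20". The Primary outcome analysis section describes the teacher SDQ as a "25-item scale used to assess behaviour in the school context".
- **Population.** The target group is young people (YP) "at risk of suspension or who are persistently absent from school", with concerns about antisocial behaviour and crime.
- **Expected reasons for loss.** In Missing data: "A summary of known reasons for missing data will be presented (e.g. YP moved school/YP excluded from school". These reasons are summarised and enter no estimate.
- **Description of missingness.** Missing cases are tabulated across the variables in the intention-to-treat (ITT) model, and a multilevel logistic model for being in that model is fitted. Both come before any threshold applies.
- **Remedy.** Remedial work needs more than 5% of baseline cases missing from the headline analysis and a statistically significant predictor of missingness. Then: "For instances where only data is missing in the teacher report SDQ externalising score outcome measure, we will add any additional covariates" identified by the screen, and the effect is re-estimated. Multiple imputation is kept for cases with a missing baseline measure.
- **MNAR.** It is listed as a category to examine by logistic regression on observed variables. No MNAR analysis follows.
- **Power.** The calculation assumes complete baseline and outcome data.

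**The concern.** The plan anticipates loss by a route that may be driven by the construct it is measuring. A YP excluded for severe externalising behaviour would probably have had a high follow-up score, and that score may be missing because it would have been high. Reach aims to reduce problem behaviour and suspensions, so this loss may also differ by arm.

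Adding covariates to a complete-case model deals with loss that those covariates explain. It does not deal with loss that still depends on the unseen follow-up score once they are in the model. Screening on observed variables cannot tell these two situations apart, and a null screen leads to no remedy at all. At stake are the headline effect size and its confidence interval, which could be wrong in either direction.

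**Working it through.** **1. The plan's own figure.** Inputs from SAP Table 2 and the power section: 600 YP as 24 blocks of 25, ICC 0.13, baseline correlation r = 0.32, two-sided alpha 0.05, power 0.80, 23 df.

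- Multiplier = t(0.975, 23) + t(0.80, 23) = 2.069 + 0.858 = 2.926 (from unrounded values)
- SE = 2 × √[(1 − 0.13)(1 − 0.32²)/600] = 2 × √(0.87 × 0.8976/600) = 0.0722
- MDES = 2.926 × 0.0722 = 0.211, against the stated 0.21. With r = 0.50 and 0.60 the formula gives 0.193 and 0.178, against the stated 0.18 to 0.19.

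**2. Direct arithmetic.** The SAP gives no exclusion rates, so all rates and shifts below are assumptions. Let pC and pR be the proportions excluded in control and Reach, and let sC and sR be how much worse the excluded would have scored than those retained in the same arm. Each retained mean is too favourable by p × s, so

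expected estimate = true effect − (pC·sC − pR·sR).

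The SE uses the retained numbers: √[0.87 × 0.8976 × (1/nC + 1/nR)]. For 10% v 5% this is 270 and 285 YP, SE 0.0750. Power is from the noncentral t on 23 df. The true effect is 0.21 SD, and the shift is the same in both arms.

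| Excluded, control v Reach | Shift (SD) | Estimate (SD) | Power | Power if the same numbers were lost at random |
|---|---|---|---|---|
| 10% v 5% | 1.0 | 0.21 − 0.05 = 0.16 | 53% | 76% |
| 10% v 7% | 1.0 | 0.21 − 0.03 = 0.18 | 63% | 76% |
| 5% v 3% | 1.0 | 0.21 − 0.02 = 0.19 | 70% | 78% |
| 10% v 5% | 0.5 | 0.21 − 0.025 = 0.185 | 66% | 76% |
| 5% v 10% | 1.0 | 0.21 + 0.05 = 0.26 | overstated effect | 76% |

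In the third row, overall loss is (15 + 9)/600 = 4%. With no other losses, that is below the 5% trigger and no remedial analysis would run.

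**3. One exclusion rule in both arms.** Suppose exclusion occurs above a cut-off on a latent score correlated with the follow-up score, Reach acts only through that score, and 10% of controls are excluded. The baseline-adjusted complete-case estimate (simulated, 4 million records) is:

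| Latent correlation | Estimate (SD) | Power |
|---|---|---|
| 0.4 | 0.20 | about 72% |
| 0.6 | 0.19 | about 68% |
| 0.8 | 0.18 | about 61% to 62% |

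**4. Direction of bias.** A separate simulation used 1,000,000 YP, a unit-SD outcome with higher scores worse, r = 0.32, and complete-case regression on arm and baseline. A beneficial effect is negative. Monte Carlo error is about 0.002.

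| Loss mechanism | True −0.21 | True 0 |
|---|---|---|
| 10%, depends on baseline only | −0.209 | about 0 |
| Rises with follow-up score, 10% in each arm | −0.212 | about 0 |
| Rises with follow-up score, same rule in both arms, 10% overall | −0.198 | about 0 |
| Rises with follow-up score, control 12% v Reach 8% | −0.181 | +0.034 |
| Rises with follow-up score, control 15% v Reach 5% | −0.131 | +0.079 |
| Rises with follow-up score, control 8% v Reach 12% | −0.239 | −0.030 |
| Rises with follow-up score, control 5% v Reach 15% | −0.285 | −0.079 |

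Baseline adjustment removes the bias when loss depends on baseline. It does not when loss depends on the follow-up score and differs by arm.

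**The case against.** **A reader might infer that excluded YP cannot be rated.** The SAP does not say so. It gives exclusion as one example of a reason for missing data. Whether a teacher in another setting may complete the form is commonly left to the protocol, which is not shown. The sound statement is that such YP may go unrated.

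**A reader might infer that the plan biases the effect towards zero.** That is only one of the possible directions. It needs Reach to work and either to lower exclusion or to face the same exclusion rule as control. With more loss in Reach, the bias runs away from zero. The SAP's stated aim concerns suspensions. It reports no exclusion rate and does not say that Reach prevents exclusion.

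**A reader might infer that nothing in the plan would reveal the problem.** That is wrong. The tabulation covers variables in the ITT model, and Table 3 lists arm among them. With 30/300 v 15/300 missing, an uncorrected chi-square test gives p = 0.02, so the screen would probably flag it. For 10% v 7% and 5% v 3%, p is about 0.19 and 0.21, but the table would still show the difference. Suspensions, attendance and offending are also compared by arm without a teacher rating. However, seeing a difference does not correct the estimate. Arm is already in the model, so finding that it predicts missingness adds nothing to the model.

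**The low baseline correlation is not itself the cause.** The pilot result, "giving an updated participant level correlation of 0.32 (calculated from the full set of pilot data", leaves about 90% of follow-up variance unexplained by baseline, so baseline is a weak stand-in for a missing rating. With the same 0.32, however, loss that depends only on baseline produced no bias. The problem is dependence on the unseen outcome, which is plausible here but not shown.

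**Conclusion.** The gap is real. The plan anticipates loss through exclusion, limits its response for a missing outcome to a doubly conditional covariate adjustment on complete cases, and names MNAR without analysing it.

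The size and sign are uncertain. Under the assumed attenuating scenarios, a true 0.21 SD becomes 0.16 SD (10% v 5% excluded, 1 SD worse) to 0.20 SD (one rule in both arms, latent correlation 0.4), with power of about 53% to 72%. The lower end needs both a twofold difference in exclusion and a full 1 SD shift. The mirror case, 5% v 10%, inflates the estimate to 0.26 SD. Bias is negligible if loss depends only on baseline, or if rates are equal and the excluded differ from the retained by the same amount in each arm.

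This does not invalidate the headline analysis. It supports a prespecified sensitivity analysis, and the uncertain direction strengthens that case.

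**What to change.** In the SAP's Missing data section:

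1. Report missing primary outcomes and their recorded reasons (excluded, moved, other) by arm, beside the primary result.
2. Prespecify a sensitivity analysis that runs regardless of the 5% and significance triggers. Multiply impute the missing outcome separately by arm, with baseline teacher and self-report SDQ, school, suspensions and attendance as auxiliary variables. Then add a range of shifts, for example 0, 0.25, 0.5, 1.0 and 1.5 SD, to YP missing through exclusion.
3. Let the shifts differ by arm. A common shift moves the estimate only by (pC − pR) × shift, which is nothing when exclusion rates are equal. With 10% excluded in each arm, shifts of 1.0 SD in control and 0.5 SD in Reach move it by 0.10 × 1.0 − 0.10 × 0.5 = 0.05 SD.
4. Report the tipping point, that is, the combination of shifts at which the conclusion changes.
5. Vary the missing-at-random assumption for YP who moved school, since the SAP gives no ground for taking it as given.

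The headline analysis is unchanged. The cost is one paragraph and a little extra analysis: the reasons, suspensions and attendance are already due to be collected, and Stata's imputation commands are already planned. The downside is that the result is also shown as a range.

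### As written, the missing-data rule cannot change the estimate when only the outcome is missing, acts only on a significant screen, and leaves MNAR loss untested

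*SAP*

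**What the plan says.** The Missing data section starts with description: reasons for loss (its examples are "YP moved school/YP excluded from school") and a multilevel logistic model of inclusion in the ITT analysis, whose covariates include age, gender and ethnicity. No action is attached to that model.

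A conditional rule follows, triggered "If over 5% of cases in the baseline sample are missing from the headline ITT analysis". Its screening stage has a stated aim: "We will examine whether data is missing completely at random (MCAP), missing at random (MAR) or missing not at random (MNAR"). The method is: "Logistic regression will be used to examine whether missing data can be statistically accounted for using the other variables in the ITT analysis". Action depends on the result: "When variables are found to account for a statistically significant proportion of variation in missing data, we will proceed to one of the next two" options.

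- If only the primary outcome is missing: "we will add any additional covariates that were found from the screening stage to the final ITT model and re-estimate the effect size".
- If the baseline is missing and the screen has found predictors of that: "we will construct a Multiple Imputation model using all variables listed for stage 1", run "to create 20 imputed data sets".

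Table 3 gives the ITT model: arm, baseline teacher SDQ externalising score and school-mean baseline score. The Analysis section adds a random intercept for school.

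**The concern.** Three features of the rule weaken it as a check on the primary estimate.

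- **Circular remedy.** The screen looks only at variables that the model already contains, so it has nothing to add when the outcome is missing. An unchanged estimate could then be reported as robustness.
- **Significance decides whether anything is done.** A non-significant screen does not show that data are missing completely at random (MCAR). Young people who lack only a baseline score then stay out of the analysis although their outcome was observed.
- **Missing not at random (MNAR) is named but not handled.** Observed data cannot separate missing at random (MAR) from MNAR, and no MNAR analysis is planned. Yet exclusion from school is plausibly related to a primary outcome built from conduct and hyperactivity scores.

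This matters because the headline ITT analysis is in practice a complete-case analysis: the Missing data section codes some cases as not in the ITT model. Baseline adjustment absorbs little, since the pilot pre/post correlation is 0.32 (R² = 0.10, Table 2). If the control arm loses more of its high-scoring young people, complete cases understate the benefit of Reach. The reverse pattern overstates it.

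**Working it through.** **1. Yardstick.** Inputs from Table 2 and the formula beneath it: J = 24, n = 25, ICC = 0.13, r = 0.32, two-sided alpha 0.05, power 0.80, 23 df.

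MDES = 2 × M × √[(1 − ICC)(1 − r²)/(Jn)], with M ≈ 2.07 + 0.86 = 2.93.

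√[(0.87 × 0.8976)/600] = 0.0361, and 2 × 2.93 × 0.0361 ≈ 0.211. The SAP prints 0.21. With r = 0.50 and 0.60 the formula gives 0.193 and 0.178, against a printed 0.18–0.19. The figures reproduce. The point does not depend on them; 0.21 only gives scale.

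**2. The rule traced through, on its literal text.**

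| Missing | Screen | Planned action | Effect on the estimate |
|---|---|---|---|
| Outcome only | Significant | Add covariates found | None: arm, baseline and school mean are already in the model |
| Outcome only | Not significant | None | None |
| Baseline | Significant | Multiple imputation, 20 sets | Can change it; assumes MAR |
| Baseline | Not significant | None | Cases with an observed outcome stay out |

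In the first row, adding a column that the model already holds leaves its fitted values and the arm coefficient unchanged.

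**3. Simulation of outcome-only loss.** 600 young people in 12 schools, ICC 0.13, r = 0.32, true effect 0, about 13% of outcomes missing, 1,500 runs, school fixed effects standing in for the random intercept. The loss rate, the mechanisms and an auxiliary variable correlated about 0.4 with the outcome are assumptions. Bias is Reach minus control in SD units; higher scores are worse. The Monte Carlo standard error is about 0.002. The SAP gives no alpha for the screen, so 0.05 was used.

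| Assumed loss mechanism | Complete case | After SAP rule | Using the auxiliary | Overall screen significant |
|---|---|---|---|---|
| MCAR | −0.003 | −0.003 | −0.003 | about 5% |
| Depends on baseline only | 0.002 | 0.002 | 0.002 | 99% |
| Control loss depends on the auxiliary | 0.039 | 0.039 | −0.005 | 5% |
| Control loss depends on the outcome (MNAR) | 0.095 | 0.095 | about 0.08 | 16% |

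The estimates before and after the rule never differed by more than rounding error (about 2 × 10⁻¹⁴). If the screen counts as positive when any single predictor has p < 0.05, the last column becomes 15%, nearly 100%, 15% and 28%. Either way, the screen is nearly always positive where the complete-case estimate is already sound, and usually negative where it is biased.

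**4. Cases available to the screen.** At the trigger, 5% × 600 = 30 missing cases. A non-significant result from so few says little.

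**5. Illustrative size.** If lost young people score δ worse than those retained, by the same amount in both arms, bias = δ × (loss in control − loss in Reach).

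- δ = 1 SD, 5-point difference: 1 × 0.05 = 0.05 SD, and 0.05/0.21 ≈ 0.24 of the MDES.
- δ = 1 SD, 10-point difference: 1 × 0.10 = 0.10 SD, and 0.10/0.21 ≈ 0.48.
- δ = 0.5 SD, 10-point difference: 0.5 × 0.10 = 0.05 SD.
- Equal loss with an equal gap: 0.

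**The case against.** The strongest reply is that the circularity comes from reading one sentence too literally. The preceding model of ITT inclusion uses age, gender and ethnicity. The word *additional* and the otherwise undefined label *stage 1* make best sense if they refer to that model. On that reading the remedy does bring in new variables and imputation does have auxiliaries. This is plausible, and it means a reader should not conclude that the authors meant to exclude every auxiliary. It does not settle the matter: the screening stage names the ITT variables, the earlier model leads to no action, and two analysts could follow the text differently. Even on the generous reading, attendance, suspensions, self-report SDQ and SRDS are left out, and the significance condition remains.

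Three further replies stand in part.

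- A reader might infer that the SAP claims its screen can identify MNAR. It says only that it will examine this, and neither branch depends on an MNAR verdict. The fault is an aim that the method cannot meet, with nothing else planned in its place.
- A reader might infer that the whole plan can only repeat the headline figure. That holds for outcome-only loss. Imputation can restore cases with a missing baseline and so move the estimate.
- Complete cases are not biased merely because data are missing. When outcome loss depends only on arm and baseline, the model already deals with it, as the second row of the simulation shows.

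The rule is also a conditional sensitivity procedure. It does not alter the headline model, and the planned tabulation of reasons for loss may make differential exclusion visible.

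**Conclusion.** The point holds and should be fixed. On its literal text the outcome-missing remedy is uninformative, the significance condition is a poor basis for deciding whether to act, and MNAR loss is left without a sensitivity analysis.

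The identity between the headline and re-estimated effects is exact, but only for outcome-only missingness and only if the screening list is the Table 3 list. The size of any bias is unknown: the SAP gives no attrition rate, no difference between arms and no score gap. The 0.05 to 0.10 SD range rests wholly on an assumed 5 to 10 point difference in loss and an assumed 1 SD gap; the simulated 0.039 and 0.095 likewise rest on assumed mechanisms. A reader might infer that the primary result will be biased by about that much, or in a known direction. The document supports neither inference.

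**What to change.** Replace the conditional rule with the following.

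- **Multiple imputation.** If more than 5% are missing, run it as a sensitivity analysis whatever the screening p-values, for missing outcomes and missing baselines alike. Keep young people whose only gap is the baseline.
- **Named variables.** Use the ITT variables, school, and auxiliaries the SAP says are collected: age, sex, ethnicity, baseline attendance, prior suspensions, baseline self-report SDQ and SRDS, and trial stage (pilot or efficacy). If age, gender and ethnicity were the intended additional covariates all along, say so. Define or drop the stage 1 label.
- **MNAR.** Add a simple delta-adjusted analysis that shifts imputed externalising scores and lets the shift differ by arm. Auxiliaries are no substitute: in the simulation they reduced the MNAR bias only from 0.095 to about 0.08.
- **Wording.** Replace the statement that screening examines MNAR with one saying that MNAR is addressed by the delta-adjusted analysis. Keep the missingness regressions as description.

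Whether to impute separately by arm, and which shifts to use, are design choices for the trial team; they should be fixed before outcomes are analysed. The cost is SAP wording and modest extra programming. No new data are needed.
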